### 2.4 Sample Size Consideration

This study randomizes up to 375 eligible patients at up to 75 sites in North America and Europe on a 2:1 randomization

THIS DOCUMENT CONTAINS CONFIDENTIAL AND PROPRIETARY INFORMATION OF EDWARDS LIFESCIENCES, LLC. IT MUST NOT BE REPRODUCED OR DISCLOSED TO THIRD PARTIES WITHOUT PRIOR WRITTEN PERMISSION OF EDWARDS LIFESCIENCES, LLC. (This template is required by DOC ))

	2017-05 Sta	tistical Analysis Plan			1.0   7/16/20	19
$\mathbb{E}$	Revision Date: Febr	uary 28, 2019	Rev		For Use Only by Affiliates of Edwards Lifesciences	Page 5 of 18
Edwards	Title	Statistical Analysis Plan	for	ACTIVE	2017-05	

ratio to the Edwards Cardioband System + GDMT (Device group) or to GDMT alone (Control group). Data will be available at 30 days, 6 months, 1 year, and long-term follow-up annually through 5 years is planned for all patients. Therefore, it is expected that a maximum of 600 patients will be enrolled (up to 375 pivotal patients plus up to 225 roll-in patients).

### 3. HYPOTHESIS AND STUDY ENDPOINTS

Transcatheter mitral valve repair with the Edwards Cardioband System, combined with GDMT will reduce MR and improve MR symptoms and functional capacity in patients with functional MR as compared with GDMT alone.

### 3.1 Co-Primary Hypothesis 1

 $H_0: P_{Device}(T=1) - P_{Control}(T=1) = 0 \\ H_1: P_{Device}(T=1) - P_{Control}(T=1) \neq 0$ 

where

H₀	= Null hypothesis
H1	= Alternative hypothesis
P Device	= Proportion of patients in the Device group with $MR \le 2+$
PControl	= Proportion of patients in the Control group with MR $\leq 2^{-1}$
т	= Time (years)

The co-primary hypothesis 1 tests the superiority in reducing MR of the Device group relative to the Control group via two independent proportions z-test with two-sided alpha = .05.

### 3.2 **Co-Primary Hypothesis 2**

 $H_0$ : The hierarchical composite ranking of the co-primary endpoints 2 does not differ by treatment  $H_1$ : The hierarchical composite ranking of the co-primary endpoints 2 does differ by treatment

The co-primary hypothesis 2 tests the superiority of the Device group relative to the Control group for the hierarchical sequence of the four co-primary endpoints 2 (see section 2.2) via the Finkelstein-Schoenfeld test (Finkelstein and Schoenfeld, 1999). The Finkelstein-Schoenfeld test is a generalization of the Gehan Wilcoxon test. See statistical analysis in section 3 for details.

### 3.3 **Primary Efficacy Endpoints (1 Year)**

- a. Co-primary efficacy endpoint 1: Prevalence of MR  $\leq$  2+ at 1 year
- b. Co-primary efficacy endpoint 2:
  - i. Time to all-cause death
  - ii. Number of heart failure hospitalizations
  - iii. Improvement in Six Minute Walk Test (6MWT) relative to baseline (≥ 40 meters improvement)
  - iv. Improvement in Kansas City Cardiomyopathy Questionnaire (KCCQ) relative to baseline (≥ 10 points improvement)

Co-primary efficacy endpoint 1 must meet statistical significance in order to proceed to co-primary efficacy endpoints 2. This approach does not require any adjustment for multiplicity. The co-primary efficacy endpoints were chosen in order to capture the ability of the Edwards Cardioband System to effectively reduce MR (co-primary endpoint 1) and improve clinical outcomes (co-primary endpoints 2).

THIS DOCUMENT CONTAINS CONFIDENTIAL AND PROPRIETARY INFORMATION OF EDWARDS LIFESCIENCES, LLC. IT MUST NOT BE REPRODUCED OR DISCLOSED TO THIRD PARTIES WITHOUT PRIOR WRITTEN PERMISSION OF EDWARDS LIFESCIENCES, LLC. (This template is required by DOC

	2017-05 Sta	tistical Analysis Plan I			1.0   7/16/20	19
E	Revision Date: Febr	uary 28, 2019	Rev		For Use Only by Affiliates of Edwards Lifesciences	Page 6 of 18
Edwards	Title	Statistical Analysis Plan	for	ACTIVE	2017-05	

### 3.4 **Primary Safety Endpoints – Device Group Only (30 Days)**

Overall rate of device and procedure related major adverse events (MAEs), which includes:

- a. Death
- b. Stroke
- c. Myocardial infarction
- d. Pericardial effusion requiring drainage
- e. Left circumflex coronary artery injury requiring intervention
- f. Mitral valve reintervention
- g. Access site and vascular complications requiring intervention

The primary safety endpoints were chosen to detect any concerns relating to safety of the Edwards Cardioband System implantation procedure.

### 3.5 Secondary Safety Endpoints – Device Group Only (30 Days)

Individual rates of the following adverse events:

- a. Death
- b. Stroke
- c. Myocardial infarction
- d. Pericardial effusion requiring drainage
- e. Left circumflex coronary artery injury requiring intervention
- f. Mitral valve reintervention
- g. Access site and vascular complications requiring intervention
- h. Need for a new permanent pacemaker

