17.	Any recent percutaneous coronary, carotid, endovascular intervention, carotid surgery, or cardiac surgery;	Within 30 days prior to procedure date		
18.	Recent implant or revision of any rhythm management device (i.e., pacemaker, cardiac resynchronization therapy [CRT] with or without cardioverter-defibrillator [CRT-D]);	Within 90 days prior to signing informed consent		
19.	Resting systolic blood pressure < 90 or > 160 mmHg after repeated measurements;	Repeated = 3 consecutive		

Exclusion Criteria #	Criteria	Window/Guidanc e
		measurements
20.	Recent CVA or TIA;	Within 30 days prior to procedure date
21.	Previous stroke with permanent disability (modified Rankin score > 2);	
22.	Severe renal insufficiency with eGFR ≤ 25 mL/min or requiring chronic renal replacement therapy;	
23.	Contraindication to transseptal catheterization;	
24.	Concurrent medical condition with a life expectancy of less than 12 months in the judgment of the investigator;	
25.	Pregnant or planning pregnancy within next 12 months; ¹	
26.	Known bleeding or clotting disorders or patient refuses blood transfusion;	
27.	Severe COPD in whom the primary mechanism of dyspnea is pulmonary disease rather than heart failure;	
28.	Recent myocardial infraction (per WHO definition);	Within 30 days prior to procedure date
29.	Patient has been approved to participate and is currently enrolled in, or has participated in another investigational drug or device clinical study where the primary study endpoint was not reached at time of enrollment;	

 $^{^{}m 1}$ Female patients of childbearing potential need to have a negative pregnancy test performed within 14 days prior to intervention and be adherent to an accepted method of contraception

Exclusion Criteria #	Criteria	Window/Guidanc e
30.	Any condition, in the opinion of the Investigator, making it unlikely the patient will be able to complete all protocol procedures (including compliance with guideline directed medical therapy) and follow-up visits;	
31.	Other medical, social, or psychological conditions that preclude appropriate consent and follow-up, including patients under guardianship.	

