Patients with a documented intolerance to Guideline Directed Medical Therapy (GDMT) will be eligible for study inclusion. All patients (i.e. whether assigned to Device and Control groups) shall continue to receive stable Guideline Directed Medical Therapy as directed by current heart failure guidelines (including use of cardiac resynchronization therapy, as indicated).^{27,28} This implies that the GDMT regimen in principle remains unchanged until primary efficacy endpoint, unless medically warranted. Changes to GDMT (doubling or halving of dose) will be documented including whether these occurred due to improvement, deterioration, or no change in the patient's condition. Medical management should continue under the direction of a heart failure specialist at regular intervals according to current heart failure guidelines.^{27,28}

FOLLOW-UP EVALUATIONS

Follow-up evaluations will be scheduled for 30 days, 180 days, 1 year, 2 years, 3 years, 4 years, and 5 years.

- For patients assigned to the Device group, the follow-up visits are scheduled based on the date of the Edwards Cardioband System index procedure.
- For patients assigned to the Control group, the follow-up visits are scheduled based on the date of randomization.
- Note: A patient in the Control group may be offered an opportunity to receive an Edwards Cardioband System after they have been followed for a minimum of 1 year and completed their primary efficacy endpoint assessment. At the time of their 1 year follow-up visit, if the patient chooses to receive the investigational device, they will be evaluated in accordance with the eligibility criteria (including concurrence by the site Heart Team and the CSC). If the patient is still eligible for enrollment, he/she will be offered an opportunity to receive the device. If the patient receives the Edwards Cardioband System implant, he/she shall be followed in accordance with the clinical

protocol schedule or at a minimum for two years if the product has received PMA Approval. This group shall be summarized as a separate cohort.

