### 3.9 Long Term Outcomes (Through 2, 3, 4, 5 Years)

The following outcomes will be collected yearly at 2 to 5 years:

- a. NYHA
- b. SMWT
- c. Heart failure hospitalizations
- d. Cardiovascular death
- e. Surgical mitral valve replacement or surgical repair
- f. Transcatheter based mitral valve interventions
- g. All-cause mortality
- h. Cardiac transplantation
- i. Mechanical hemodynamic support (e.g., LVAD)
- j. Number of days alive and out of hospital
- k. NT-proNBP level
- I. Need for new permanent pacemaker
- m. KCCQ
- n. SF-36

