### 6. DATA AND ANALYSIS CONVENTIONS

### 6.1 General Conventions

All data collected will be summarized overall and by treatment groups.

For continuous variables (e.g., age, percent diameter stenosis, and lesion length), results within treatment group will be summarized with the numbers of observations, means, medians, standard deviations, minimums, maximums, and 95% confidence intervals per table mockups. Differences between the treatment groups, where specified, will be summarized with the differences of the two means and 95% confidence intervals for the difference between the means, and p-values based on a t-test. The distributions within each group will be tested for normality using the Shapiro-Wilks test and if normality cannot be assumed then a Wilcoxon rank-sum test and 95% confidence interval of the median will be presented. The confidence interval for the difference of two means will be calculated under the assumption of unequal variances.

For categorical variables (e.g., gender, in-hospital event rates, and angina status), results within treatment group will be summarized with patient counts and percentages. Differences between the two treatment groups, where specified, will be

THIS DOCUMENT CONTAINS CONFIDENTIAL AND PROPRIETARY INFORMATION OF EDWARDS LIFESCIENCES, LLC. IT MUST NOT BE REPRODUCED OR DISCLOSED TO THIRD PARTIES WITHOUT PRIOR WRITTEN PERMISSION OF EDWARDS LIFESCIENCES, LLC. (This template is required by DOC ))

	2017-05 Sta	tistical Analysis Plan			1.0   7/16/20	19
	Revision Date: Febr	uary 28, 2019	Rev		For Use Only by Affiliates of Edwards Lifesciences	Page 10 of 18
Edwards	Title	Statistical Analysis Plan	for	ACTIVE	2017-05	

summarized with the difference in percentages, the asymptotic 95% confidence interval for the difference of two percentages, and a p-value based on a chi squared test. If 20% or more of the expected cell frequencies are less than 5, a Fisher's exact test will be used to test for differences in proportions.

For the determination of event rates in-hospital, the number of all patients in the patient population will be used as the denominator. For variables ascertained at follow-up, the denominator will be only those patients who had follow-up performed at that time point. Unless otherwise noted, patients with missing data are excluded from the denominator.

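### The new-pacemaker rate has no at-risk denominator and no definition, and the default denominators keep patients who already have a pacemaker or CRT

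*SAP*

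**What the plan says.** SAP 3.5 introduces its list as "Individual rates of the following adverse events" and ends it with "Need for a new permanent pacemaker", for the Device group only, through 30 days. Protocol 5.3 has the same item. SAP 3.9 item l, "Need for new permanent pacemaker", carries it into the outcomes for years 2 to 5. Protocol Appendix B contains no definition of a new permanent pacemaker.

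On who can enter, exclusion 18 in Protocol 6.3 covers "Recent implant or revision of any rhythm management device", with the window "Within 90 days prior to signing informed consent". No criterion excludes an older device. Protocol 8.3 describes background medical therapy for both arms as "including use of cardiac resynchronization therapy, as indicated", so CRT users are expected in the trial.

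On denominators, SAP 6.1 says that for in-hospital event rates "the number of all patients in the patient population will be used as the denominator". For variables measured at follow-up it uses patients with follow-up at that time point, and it summarises post-discharge results by Kaplan-Meier. Protocol 13.4.1 has the same rules.

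On the analysis, Protocol 13.4.3 promises rates with 95% confidence intervals for the secondary safety endpoints. SAP 8.3 names those endpoints in its heading, but its text covers only the major adverse event rate and its components. New pacemaker is not one of those components (SAP 3.4).

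**The concern.** A rate of new pacemakers is informative for patients who do not yet have one. If patients who already have a pacemaker or CRT count in the denominator but contribute few or no events, the figure is too low for the patients it is meant to inform. It also moves with the baseline device mix, whatever the procedure does.

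The 30-day endpoint has no concurrent control, so randomisation cannot cancel the effect: the rate and its interval are the whole result. Table 7 in Protocol Appendix A lists conduction disorders that may lead to a permanent pacemaker, so this is a risk that readers of the results will look up. The roll-in and pivotal cohorts are reported separately, and their rates could differ only because their baseline device shares differ.

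**Working it through.** The plan states no pacemaker rate, threshold or denominator count, so there is no figure to reproduce. The check has two parts: whether any rule removes patients with a device, and how large the effect would be.

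**Does any rule remove them?**

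- In-hospital default (SAP 6.1): all patients in the population. Patients with a device stay in.
- Follow-up default (SAP 6.1): patients seen at that time point. Patients with a device stay in.
- Post-discharge default (SAP 6.1): Kaplan-Meier. They stay in the risk set. With no censoring before 30 days the estimate equals the simple proportion, so the dilution is the same.
- Endpoint-specific text (SAP 3.5, 3.9, 8.3, 8.7; Protocol 5.3, 5.7, 13.4.3): no restriction.

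A 30-day endpoint spans the hospital stay and the time after discharge, so it is not clear which default applies. Each one keeps patients with a device.

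**How large is the effect?**

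Inputs:

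- Device group: 375 x 2/3 = 250 patients (375 randomised at 2:1, Protocol section on study design).
- f, the share with a pacemaker or CRT at baseline: not in the documents; assumed 10% to 50%.
- Events: 10 new pacemakers, assumed for illustration, all in patients without a device.

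Let r0 be the rate in patients without a device and r1 the rate in patients with one. Then

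all-patient rate = (1 - f) x r0 + f x r1.

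With r1 = 0 this is (1 - f) x r0, so the at-risk rate is 1/(1 - f) times the all-patient rate. The all-patient rate is 10/250 = 4.0% (exact 95% CI 1.9 to 7.2) in every row below.

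| f (assumed) | At-risk n | At-risk rate (exact 95% CI) | Ratio 1/(1 - f) |
|---|---|---|---|
| 10% | 225 | 4.4% (2.2 to 8.0) | 1.11 |
| 20% | 200 | 5.0% (2.4 to 9.0) | 1.25 |
| 30% | 175 | 5.7% (2.8 to 10.3) | 1.43 |
| 40% | 150 | 6.7% (3.2 to 11.9) | 1.67 |
| 50% | 125 | 8.0% (3.9 to 14.2) | 2.00 |

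Read the other way, an assumed at-risk rate of 10% would be reported as 10% x 0.8 = 8% at f = 20% and 10% x 0.6 = 6% at f = 40%.

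**What if patients with a device can have the event?** The all-patient rate divided by the at-risk rate is (1 - f) + f x (r1/r0). At f = 30% with r1 half of r0, it is 0.70 + 0.30 x 0.5 = 0.85, against 0.70 with r1 = 0. There is no dilution if r1 = r0. The size therefore depends on the missing definition as well as on f.

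**The case against.** The strongest case against has five parts.

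- A reader might infer that the plan divides this endpoint by all patients. It does not say so. That denominator is the default for in-hospital rates only. What stands is that no at-risk denominator is set and every default keeps patients with a device.
- A reader might infer that such a patient cannot need a new pacemaker. The documents do not support this. The term is undefined, and an upgrade or a replacement system could be counted. Appendix B also says that the Clinical Events Committee Charter will refine the endpoint definitions and prevails over the protocol. That charter and the table mock-ups are not among the documents, so either might settle the matter. Until one does, the SAP leaves it open.
- Table 7 does not tie conduction disorders to annular anchoring. It lists events that may come from the device, the procedure, tests or ancillary procedures, or from heart failure over time. The point does not need that link.
- For years 2 to 5, SAP 8.7 compares the randomised arms. Randomisation should balance the baseline device mix, so both arms' rates shrink by about the same factor and the relative comparison is largely kept. This limits the long-term concern mainly to absolute rates.
- The all-patient rate is a legitimate quantity, incidence per patient in the population, and no decision hangs on this endpoint. That is why it should be kept as a second figure, and why the point is a reporting improvement.

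**Conclusion.** The concern holds as a gap in definition and denominator. Patients with an older pacemaker or CRT are eligible, and nothing in the plan takes them out of the new-pacemaker rate. If they have the event less often than other patients, the 30-day Device-group rate understates the risk for patients without a device. The factor is about (1 - f) if they have it rarely or never.

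The size cannot be determined from the documents. The ratio of 1.11 to 2.0 rests on an assumed f of 10% to 50% and on no events among patients with a device, so it should not be read as demonstrated bias. The endpoint lies outside the primary safety composite and has no hypothesis or performance goal, so alpha, power and trial success are unaffected.

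**What to change.** 1. In SAP 8.3, add analysis text for this endpoint, which the section's text omits. In SAP 8.7, add the same rule for the long-term outcome.
2. Define a new permanent pacemaker, stating how upgrades, replacements and patients with only an ICD at baseline are counted. Make the definition agree with the Clinical Events Committee Charter.
3. Report the rate with its 95% confidence interval among patients without a permanent pacemaker or CRT at baseline, and the all-patient rate with its interval beside it.

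No new visit or test should be needed. Medical history is collected at baseline (Protocol 6.6), prior conditions and interventions are tabulated from the case report form (SAP 7.3), and sites must already check device history to apply exclusion 18. This assumes that the form records pacemaker and CRT status, which should be confirmed. The cost is a few sentences in the SAP, a smaller denominator with a wider interval, and a less favourable figure.

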### 3.6 Secondary Endpoints – Powered (1 Year)

The following key secondary efficacy endpoints will be tested between Device and Control group in hierarchical order to account for multiplicity:

- a. MR ≤ 1+
- b. NYHA class
- c. KCCQ
- d. 6MWT
- e. SF-36v2 Health Survey (SF-36)
- f. Heart failure hospitalizations
- g. Cardiovascular death
- h. All-cause mortality

### 3.7 Other Secondary Endpoints

The following outcomes will be assessed between Device and Control, where appropriate:

For the Device Arm:

1. Device Success (measured at 30 days): Device is deployed as intended and the delivery system is successfully retrieved as intended at the time of the patient's exit from the cardiac catheterization laboratory (per device analysis).

THIS DOCUMENT CONTAINS CONFIDENTIAL AND PROPRIETARY INFORMATION OF EDWARDS LIFESCIENCES, LLC. IT MUST NOT BE REPRODUCED OR DISCLOSED TO THIRD PARTIES WITHOUT PRIOR WRITTEN PERMISSION OF EDWARDS LIFESCIENCES, LLC. (This template is required by ))

	2017-05 Sta	tistical Analysis Plan		8	1.0   7/16/20	19
E	Revision Date: Febr	uary 28, 2019	Rev		For Use Only by Affiliates of Edwards Lifesciences	Page 7 of 18
Edwards	Title	Statistical Analysis Plan	for	ACTIVE	2017-05	

2. Procedural Success (measured at 30 days): Device success with evidence of MR reduction  $\leq$  2+ at discharge and without the need for a surgical or percutaneous intervention prior to hospital discharge (per patient analysis).

3. Clinical Success (measured at 30 days): Procedural success with evidence of MR reduction  $\leq$  2+ and without MAEs\* at 30 days (per patient analysis).

\*Major adverse events (MAE) defined as death, stroke, myocardial infarction, pericardial effusion requiring drainage, left circumflex coronary artery injury requiring intervention, mitral valve reintervention and access site and vascular complications requiring intervention.

4. Responder analysis percentage of patients who achieve:

- a. MR  $\leq$  2+ and
- b. Meets at least two of the following criteria:
  - i. Improvement vs. baseline in symptoms (e.g., NYHA Class improvement  $\geq$  1)
  - ii. Improvement vs. baseline in functional status (6MWT improvement ≥ 30 meters)
  - iii. Improvement vs. baseline in QoL (KCCQ improvement ≥ 5 points)

For both the Device and Control Arms:

- 1. Patient success (measured at 1 year) is defined as
  - a. Patient remains alive and stroke free,
  - b. No re-hospitalizations (or equivalents) for HF, and
  - c. Patient meets at least two of the following criteria:

i. Improvement vs. baseline in symptoms (e.g., NYHA Class improvement  $\ge 1$ ) ii. Improvement vs. baseline in functional status (6MWD improvement  $\ge 30$  meters) iii. Improvement vs. baseline in QoL (KCCQ improvement  $\ge 5$  points)

2. Mean daily steps (measured at 1 year):

Mean daily steps measured during the hours of 6am to 10pm, via an activity monitoring device, during a one month collection period following the 1 year follow-up visit. Patient Success (evaluated at 1 year post index procedure).

#### 3.8 Echocardiography Endpoints (Annually Through 5 Years)

Key echocardiography parameters by echo core lab assessment at 30 days, 6 months, and yearly at 1 to 5 years:

- a. MR severity
- b. LVEDVi
- c. LVESVi
- d. TAPSE
- e. Mitral valve effective orifice area (EOA)
- f. Left ventricular ejection fraction (LVEF)
- g. Stroke volume
- h. Left atrial volume
- i. Tricuspid regurgitation severity
- j. Estimated pulmonary artery pressure

THIS DOCUMENT CONTAINS CONFIDENTIAL AND PROPRIETARY INFORMATION OF EDWARDS LIFESCIENCES, LLC. IT MUST NOT BE REPRODUCED OR DISCLOSED TO THIRD PARTIES WITHOUT PRIOR WRITTEN PERMISSION OF EDWARDS LIFESCIENCES, LLC. (This template is required by )

	2017-05 Sta	tistical Analysis Plan			1.0   7/16/20	19
$\mathbb{E}^{\mathbb{P}}$	Revision Date: Febr	uary 28, 2019	Rev		For Use Only by Affiliates of Edwards Lifesciences	Page 8 of 18
Edwards	Title	Statistical Analysis Plan	for	ACTIVE	2017-05	

### 3.9 Long Term Outcomes (Through 2, 3, 4, 5 Years)

The following outcomes will be collected yearly at 2 to 5 years:

- a. NYHA
- b. SMWT
- c. Heart failure hospitalizations
- d. Cardiovascular death
- e. Surgical mitral valve replacement or surgical repair
- f. Transcatheter based mitral valve interventions
- g. All-cause mortality
- h. Cardiac transplantation
- i. Mechanical hemodynamic support (e.g., LVAD)
- j. Number of days alive and out of hospital
- k. NT-proNBP level
- I. Need for new permanent pacemaker
- m. KCCQ
- n. SF-36

